Clinical study protocol

Program name: Ultrasound-guided serratus anterior plane block combined with erector spinae plane block versus thoracic paravertebral block for postoperative analgesic effect and recovery after thoracoscopic surgery

NCT number: 1000012129

Date of applicant: August 29, 2022

1. Research Background and Significance:

Thoracoscopic surgery is becoming increasingly popular because it has several advantages compared with thoracotomy of small incision, fast postoperative recovery, fewer perioperative complications, short hospital stay, and improved postoperative quality of life.^[1] However, patients are still faced with moderate to severe pain after thoracoscopic surgery. How to control pain effectively and promote postoperative recovery is still a challenging problem.^[2-3]

Opioids usage, epidural analgesia, thoracic paravertebral block, intercostal nerve block, erector spinal plane nerve block, and serratus anterior plane block are commonly used to control pain after thoracoscopic surgery. Although the use of opioid analgesics can effectively control pain, with the increase of the dose of opioids, the adverse effects will become more pronounced, such as respiratory depression, which is not conducive to the postoperative recovery. Regional anesthesia techniques are more effective in relieving pain than opioids alone and can reduce opioid dosage, thus helping to reduce opioid-related adverse effects.^[4] Epidural analgesia was once considered as the gold standard for post-thoracotomy pain control,^[5] but it is not widely used for pain management after thoracoscopic surgery because it is related to high potential risks of nerve lesions, rupture of spinal dura mater, epidural hematoma, hypotension and difficult to operate for the inexperienced.

Thoracic paravertebral block is effective in controlling pain after thoracoscopic surgery, but it also carries risks such as difficulty of operation and perforation of the pleura. Intercostal nerve block has a certain effect on postoperative pain control after thoracotomy,^[6-7] and has the advantages of safe and simple operation, but its analgesia time is short and it is difficult to relieve visceral pain. In recent years, erector spinae plane block and serratus anterior plane block have been applied to postoperative thoracoscopic analgesia.^[7-8] They are easy to operate and far away from the spinal cord and pleura and other important tissues, but they are still lacking in analgesic effect compared with thoracic paravertebral block. Single erector spinae plane block or serratus anterior plane block is difficult to replace thoracic paravertebral block in postoperative analgesia. Therefore, it is of great significance to find a simple and sufficient analgesic nerve block to replace the thoracic paravertebral block with many risks.

ESPB is a new technique used to provide thoracic anesthesia, and in clinical trials of non-inferiority tests, erector spinae plane block is non-inferior to thoracic paravertebral block in terms of analgesia,^[9] and also has a potential visceral analgesic effect.^[10] SAPB was first used in breast surgery and is now commonly used in cardiothoracic surgery.^[11] SAPB, as part of a multimodal analgesia, is a non-inferior regional anesthesia technique compared to PVB in terms of analgesic efficacy, especially in reducing opioid use.^[12] Postoperative analgesia can be achieved by erector spinae plane block in a variety of ways. Local anesthetics can enter the paravertebral space, diffuse along the fascial plane below the erector spinae muscle, diffuse backward to the erector spinae muscle, and also diffuse laterally.^[13] However, compared with thoracic paravertebral block, the diffusion of local anesthetics in the paravertebral space is limited. Serratus anterior plane block could

block the lateral cutaneous branches of intercostal nerves, the long thoracic nerve and the thoracodorsal nerve, and the dermatome of sensory block could be up to T2-9.

Therefore, from the existing clinical researchs and the principle of nerve block, it is reasonable to replace thoracic paravertebral block with serratus anterior plane block combined with erector spinae plane block for postoperative thoracoscopic analgesia.

There is no research on the analgesic effect of erector spinae plane combined with serratus anterior plane block after thoracoscopic surgery. The purpose of this study is to explore whether the serratus anterior plane block combined with erector spinae plane block can replace thoracic paravertebral block to provide better analgesic effect after thoracoscopic surgery, so this study has very important clinical significance.

2. Research purpose:

To investigate whether serratus anterior combined with spinal erector plane block can provide adequate analgesia after thoracoscopic surgery.

3 Research Design

3.1 Research Type

Single-center, prospective, randomized, double-blind, controlled study.

3.2 Sample size estimation

According to an preliminary experiment (7 patients in the serratus anterior plane block combined with erector spinae plane block group and 7 patients in the thoracic paravertebral block group), the results showed that the 24h postoperative morphine consumption was 23.7 ± 4.8 mg in the SAPB & ESPB group and 28.7 ± 4.2 mg in the PVB group. A difference of 2.5 mg in the 24h postoperative morphine consumption was chosen as the minimum expected difference between the two groups. 1:1 enrollment would require 41 patients in each group to achieve a significance level of 0.05 for a one-sided test and performance test of 80%. A total sample size of 92 subjects was required if the dropout rate was set at 10%.

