10) After returning to the ward, the patient can press the PCA for additional analgesia according to the needs. The patient was given rescue analgesia, a single use of diclofenac sodium suppository, if the pain was not relieved or the patient requested it. Investigators conducted postoperative visits at 2h, 4h, 8h and 24h postoperatively, the dosage of PCA, the times of rescue analgesia, VAS scores at rest and cough and adverse reactions were recorded. FVC (L), FEV1 (L) and FEF 25% -75% (L/sec) were recorded for three times by spirometer in the sitting position at 4h and 24h postoperatively. Patients were assessed postoperatively using the QoR-15 Patient Questionnaire at 24h postoperatively.

6. Outcome measurements

6.1 The primary outcome :

Cumulative morphine consumption at 24h postoperatively

6.2 The secondary outcomes:

- (1) The cumulative morphine consumption at 1h, 2h, 4h and 8h postoperatively.
- (2) The times of remedial analgesia at 1h, 2h, 4h, 8h and 24h postoperatively.
- (3) VAS score at rest and cough at 1h, 2h, 4h, 8h and 24h postoperatively.
- (4) The changes of FVC (L), FEV₁ (L) and FEF 25% - 75% (L / sec) were observed before operation, 1h, 4h and 24h after postoperatively.
- (5) Changes of QoR-15 questionnaire scores before and 24h postoperatively.
- (6) Postoperative complications and rehabilitation time nodes (including drainage tube removal time, discharge time, etc.).

7 Security

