9.3 Reasons for dropout

For any dropout case, the investigator must record the reasons for the dropout. In general, there are five reasons, namely, adverse events, violation of the trial protocol, loss to follow-up (including self-withdrawal of the subject), discontinuation of the sponsor and others.

10. Statistical analysis

Measurement data were analyzed and compared by t-test or Mann-Whitney U test, depending on whether the data were distributed normally or not. Repeated measures data (e.g., morphine consumption, VAS scores, pulmonary function measures) were analyzed using one-way analysis of variance(ANOVA). Enumeration data were compared by χ^2 or Fisher's exact test. $p < 0.05$ was considered significant.

11. Summary of lab report

Unblinding is performed when the statistical analysis is completed and the statistical analysis report is written by the statistical analyst. The statistical analysis report after Unblinding shall be delivered to the main researchers of the experiment to write the research report.

12 Data preservation

The research data related to this clinical trial were kept by the Department of Anesthesiology of Tongji Hospital.

References:

1. Bendixen, M., et al., *Postoperative pain and quality of life after lobectomy via video-assisted thoracoscopic surgery or anterolateral thoracotomy for early stage lung cancer: a randomised controlled trial*. Lancet Oncol, 2016. 17(6): p. 836-844.
2. Kaplowitz, J. and P.J. Papadakos, *Acute pain management for video-assisted thoracoscopic surgery: an update*. J Cardiothorac Vasc Anesth, 2012. 26(2): p. 312-21.
3. Elmore, B., et al., *Pain Management Following Thoracic Surgery*. Thorac Surg Clin, 2015. 25(4): p. 393-409.
4. Kumar, K., et al., *A Review of Opioid-Sparing Modalities in Perioperative Pain Management: Methods to Decrease Opioid Use Postoperatively*. Anesth Analg, 2017. 125(5): p. 1749-1760.

5. Joshi, G.P., et al., *A systematic review of randomized trials evaluating regional techniques for postthoracotomy analgesia*. Anesth Analg, 2008. 107(3): p. 1026-40.
6. Zhu, M., et al., *Ultrasound-Guided Intercostal Nerve Block Following Esophagectomy for Acute Postoperative Pain Relief in the Postanesthesia Care Unit*. Pain Pract, 2018. 18(7): p. 879-883.

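### The one-sided 0.05 test that sizes the trial in Section 3.2 is not carried into Section 10; if the primary comparison is non-directional, power for 2.5 mg is about 70%, not 80%

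*Combined protocol and SAP*

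**What the plan says.** Section 3.2 takes its inputs from a pilot of 7 patients per group, with 24h morphine consumption of "23.7 ± 4.8 mg in the SAPB & ESPB group and 28.7 ± 4.2 mg in the PVB group". It then sets the target: "A difference of 2.5 mg in the 24h postoperative morphine consumption was chosen as the minimum expected difference between the two groups". From these it states that 1:1 enrolment needs "41 patients in each group to achieve a significance level of 0.05 for a one-sided test and performance test of 80" per cent, and 92 patients in total after allowing 10% dropout. This is the only place where sidedness is mentioned.

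Section 6.1 gives the primary outcome as "Cumulative morphine consumption at 24h postoperatively". Section 6.2 lists the earlier time points separately as secondary: "The cumulative morphine consumption at 1h, 2h, 4h and 8h postoperatively".

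Section 10 has two sentences that could govern the primary outcome. The general one reads "Measurement data were analyzed and compared by t-test or Mann-Whitney U test, depending on whether the data were distributed normally or not". The other reads "Repeated measures data (e.g., morphine consumption, VAS scores, pulmonary function measures) were analyzed using one-way analysis of variance(ANOVA"). Significance is declared at p below 0.05. Section 10 does not say whether that is one-sided or two-sided, states no hypothesis or direction, and does not assign a test to the primary outcome.

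**The concern.** A sample size is valid for the test it was computed for. Here the sizing test is one-sided, but the analysis section does not mention it, and the one method it links by name to morphine consumption cannot be one-sided. A reader who follows Section 10 literally, or who takes an unqualified 0.05 in the usual two-sided sense, would run a test with less power than Section 3.2 states.

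Two things are at stake. First, the chance of missing a true 2.5 mg difference would be about 30% rather than 20%. Second, the primary conclusion could depend on which section is followed: a band of plausible results is significant under one test and not under the other, and nothing written for the analysis settles which applies.

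**Working it through.** **Inputs.** From Section 3.2: difference 2.5 mg, pilot SDs 4.8 and 4.2 mg, alpha 0.05 one-sided, power 80%, 1:1 allocation, dropout 10%. The documents state no planning SD. I assume the pooled pilot value, sqrt((4.8² + 4.2²)/2) = sqrt(20.34) = 4.51 mg, and show the range from 4.2 to 4.8 mg.

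**1. Reproduce the plan's figure.** n per group = 2(z_alpha + z_beta)² SD² / difference².
- One-sided 0.05: 2 × (1.645 + 0.842)² × 20.34 / 6.25 = 40.2, so 41 per group.
- With dropout: 41/0.9 = 45.6, so 46 per group and 92 in total.

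Both stated figures reproduce, which supports the pooled SD as the planning value.

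**2. Power at 2.5 mg under each test** (noncentral t; 2n − 2 degrees of freedom):

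| Evaluable per group | SD (mg) | One-sided 0.05 | Two-sided 0.05 |
|---|---|---|---|
| 41 | 4.2 | 84.8% | 75.9% |
| 41 | 4.51 | 80.1% | 69.8% |
| 41 | 4.8 | 75.6% | 64.4% |
| 46 (no dropout) | 4.51 | 84.0% | 74.9% |

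A one-way ANOVA of the 24h values with treatment group as its factor has noncentral-F power of 69.8% at 41 per group and SD 4.51, identical to the two-sided t-test. For Mann-Whitney on normal data (efficiency 3/π) the pair is about 78% and 68%.

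**3. How the gap depends on the true difference** (41 per group, SD 4.51):

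| True difference (mg) | One-sided | Two-sided | Gap (points) |
|---|---|---|---|
| 1.0 | 25.8% | 16.8% | 9.0 |
| 1.5 | 44.0% | 31.9% | 12.1 |
| 2.0 | 63.5% | 51.0% | 12.6 |
| 2.5 | 80.1% | 69.8% | 10.2 |
| 3.0 | 91.0% | 84.5% | 6.5 |
| 3.5 | 96.7% | 93.5% | 3.2 |
| 5.0 | 99.96% | 99.86% | 0.1 |

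**4. Results on which the two tests disagree.** Standard error = 4.51 × sqrt(2/41) = 0.996 mg. With 80 degrees of freedom the critical differences are 1.664 × 0.996 = 1.66 mg one-sided and 1.990 × 0.996 = 1.98 mg two-sided. The band is 1.54 to 1.85 mg at SD 4.2, and 1.76 to 2.11 mg at SD 4.8. For example, an observed 1.8 mg gives t = 1.807, with p = 0.037 one-sided and 0.075 two-sided. If the true difference is 2.5 mg, about 10% of trials (80.1% − 69.8%) fall in the band.

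**5. What a two-sided test supports or would need.** With 41 per group, 80% two-sided power is reached at 2.82 mg (2.63 at SD 4.2, 3.01 at SD 4.8). Holding 80% for 2.5 mg needs 2 × (1.960 + 0.842)² × 20.34 / 6.25 = 51.1, so 52 per group, or 53 by the t distribution. With dropout that is 58 or 59 per group, 116 or 118 in total.

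**The case against.** The strongest reply is that Section 10 is silent rather than contradictory. Both sections use 0.05, the documents nowhere call for a two-sided test, and one-sided is the only sidedness written. Read together, the one-sided test governs and 80% stands. This is a fair reading, and the 70% figure must therefore stay conditional. It does not close the matter, because even on this reading Section 10 names neither the primary test nor its direction.

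The ANOVA route is also open to challenge. That sentence concerns repeated-measures data, and morphine consumption is only an example. The primary outcome is one cumulative value per patient, so it fits the t-test/Mann-Whitney sentence at least as well. The ANOVA factor is not named either; if it were time, the ANOVA would not be the between-group primary test and 69.8% would not be its power. Both points stand as limits. But the 24h value is also the last point of the morphine series, and the text does not separate the two.

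On weight, the pilot difference was 5.0 mg, where power exceeds 99.8% either way. The pilot SD is also imprecise: on 12 degrees of freedom, assuming normality, its 95% interval is 3.2 to 7.4 mg, which moves power from 96.6% to 44.5% one-sided and from 93.3% to 32.4% two-sided. That spread exceeds the sidedness gap. However, the plan's 80% claim is made at 2.5 mg, and two-sided power is lower at every SD.

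Two stronger readings are tempting. A reader might infer that the trial is simply underpowered, or that Section 10 prescribes a two-sided test; the documents support neither, since a one-sided t-test is not excluded and the sizing arithmetic is correct. A reader might also infer a non-inferiority design, because the same formula with a 2.5 mg margin and zero true difference again gives 41. Section 3.2 calls 2.5 mg an expected difference, Section 1 speaks of superior analgesia as well as replacement, and no margin is declared, so that match is not evidence of intent.

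**Conclusion.** The concern holds in conditional form and should be fixed. Section 3.2 is internally correct; the fault is that its test does not reach Section 10. If the 24h value is compared between groups by the ANOVA (treatment group as factor) or by a two-sided t-test at 0.05, power for 2.5 mg with 41 evaluable per group is about 70%, with a range of 64% to 76% for SDs of 4.8 to 4.2 mg. If a one-sided t-test is used, 80% holds.

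The gap is about 9 to 13 points for true differences of 1 to 2.5 mg and fades above about 3.5 mg. These figures assume approximately normal data, a common SD near the pilot value, and the planned 10% dropout. Confidence is high in the omission and the arithmetic. Whether power is actually lost depends on a choice that the documents leave open.

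**What to change.** Keep the 92 patients. In Section 10, name one primary between-group test of 24h cumulative morphine consumption, with its hypothesis, direction and sidedness, in a sentence separate from the repeated-measures ANOVA. Make Section 3.2 match, in one of two ways:

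- **Two-sided 0.05.** Restate Section 3.2 as about 70% power for 2.5 mg, or 80% power for about 2.8 mg, with 41 evaluable per group. The cost is a less favourable stated power.
- **One-sided 0.05.** This is the smaller edit, since it is the sidedness already written. State it and its direction in Section 10, use a directional test rather than ANOVA, and report the matching 90% two-sided confidence interval. The cost is a weaker evidence standard, equal to that of a two-sided 0.10 test.

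If the intended hypothesis is non-inferiority, its margin must be declared. Either route takes two or three sentences. Enlarging the trial to 116 to 118 patients would be needed only to hold 80% two-sided power at 2.5 mg (SD 4.51 mg).

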3.3 Randomization and double- blinded study

Patients were allocated randomly to SAPB & ESPB group and PVB group according to computer-generated random number table. All patients and an investigator who was responsible for follow-up during 48 postoperative hours were blinded to the randomization groups. The investigator instructed the patients to use a patient-controlled intravenous analgesia (PCA) device for postoperative pain management, the visual analog scale to assess pain at rest and during coughing, and the correct use of a pulmonary function meter.

Serratus anterior plane block combined with erector spinae plane block were performed in the experimental group after anesthesia, while thoracic paravertebral nerve block was performed in the control group .

4 Subject selection and withdrawal

4.1 Inclusion criteria:

1. American Society of Anesthesiologists (ASA) physical status I-II
2. Age from 18–75 years
3. BMI 19–28 kg/m²;
4. Selective thoracoscopic partial pneumonectomy under general anesthesia;
5. Informed consent has been signed.

4.2 Exclusion criteria:

1. Daily use of opioid analgesics or history of opioid abuse
2. Reoperation in ipsilateral thorax
3. Allergic to any of the drugs used in the study, or have a history of drug allergy
4. Have mental or nervous system diseases, motor or sensory defects;
5. Coagulation dysfunction
6. Have cognitive dysfunction, unable to cooperate with the research;
7. Severe renal, liver or heart dysfunction
8. Chest wall and spine trauma, infection, deformity and other conditions where nerve block cannot be carried out
9. Participated in other clinical trials within 3 months prior to study inclusion
10. Other reasons considered unsuitable for clinical trials by the investigator
11. Refusal to participate.

4.3 Exit criteria:

1. Conversion to thoracotomy unrelated to anesthesia;
2. The operation lasted more than 4 hours;
3. The consciousness in PACU was completely awake, and there was no effect in plane block;
4. Serious adverse events, complications or special physiological changes are not suitable for further study;
5. The patient or his/her guardian requests to withdraw;
6. Other researchers cited reasons to stop the study

5 Research process

The anesthesiologist went to the ward one day before the operation to evaluate the anesthesia of the patients who were going to undergo thoracoscopic pulmonary resection, signed the informed consent form, and selected the subjects according to the inclusion criteria and exclusion criteria. They were randomly divided into SAPB & ESPB group(test group) and PVB group(control group). Patients were also taught how to use the spirometer, patient-controlled intravenous analgesia(PCA), and visual analogue scale (VAS). (VAS: a 100 mm horizontal line, with 0 mm at one end of the line, indicating no pain. The other end is 100mm, indicating severe pain. The middle portion indicates varying degrees of pain.)

- 1) All patients were forbidden to drink and eat before operation without preoperative medication
- 2) After the patients entered the operating room, the investigator measured the

VAS score of the patient at rest and coughing in the sitting position. FVC (L), FEV₁ (L) and FEF 25% -75% (L/sec) were measured by spirometer for three times. Patients were assessed preoperatively using the QoR-15 Patient Questionnaire (see attached page).

- 3) Blood pressure, pulse, oxygen saturation and ECG were monitored. Anesthesia induction was performed after mask oxygenation: parecoxib sodium 40 mg, penehyclidine hydrochloride 0.5 mg, tropisetron 2 mg and sufentanil 0.5 μ g \cdot kg $^{-1}$, propofol 1.5–2.0 mg \cdot kg $^{-1}$ and rocuronium 0.8 mg \cdot kg $^{-1}$.
- 4) Performing tracheal intubation, ultrasound-guided radial artery cannulation to monitor ambulatory blood pressure and internal jugular central venous catheterization to establish a central venous channel.
- 5) Ultrasound-guided serratus anterior plane block combined with erector spinae plane block was performed in the experimental group. The erector spinae plane block was performed at T5 and T7 segments, with 10 ml 0.4% ropivacaine in each segment and 20 ml 0.4% ropivacaine in serratus anterior plane block. The control group received ultrasound-guided thoracic paravertebral block at T5 and T7 with 20 ml of 0.4% ropivacaine in each segment.
- 6) Anesthesia maintenance: 1-2% sevoflurane, dexmedetomidine 0.5 μ g \cdot kg $^{-1}$ \cdot h $^{-1}$ and remifentanil 0.1-0.2 μ g \cdot kg $^{-1}$ \cdot min $^{-1}$. Maintain the stability of intraoperative vital signs. Volume control ventilation mode: tidal volume was 6-8ml/kg, airway pressure was maintained within 25cmH₂O, end-expiratory CO₂ was maintained within 35-45mmHg, and lungs were dilated once every 1 hour. ECG, HR, BP, SpO₂, PetCO₂, body temperature, liquid intake and output were monitored. During the operation, vasoactive drugs were used as needed to maintain blood pressure, heart rate was maintained within \pm 20% of the preoperative basic level. Correct acid-base imbalance and electrolyte disturbance according to arterial blood gas analysis.
- 7) analgesic connection: intravenous injection of 5mg oxycodone 30 minutes before the end of surgery.
- 8) At the end of the operation, the endotracheal tube was removed when the patient was awake. Measure the level of nerve block when the patient is conscious. If there was no nerve block plane, the patient was withdrawn from the trial. The patient-controlled intravenous analgesia, which equipped with 0.5mg/ml oxycodone, 1ml/h background infusion, 3ml additional infusion and locked for 5min, was used immediately after extubation.
- 9) The patients were observed in the PACU for one hour, and the PCA could be applied for additional analgesia according to the needs of the patients. The patient was given rescue analgesia, a single intravenous dose of 2 mg of oxycodone, if the pain was not relieved or the patient requested it. Patients took a sitting position and measured the VAS scores of the patients at rest and coughing at 1h postoperatively. FVC (L), FEV₁ (L) and FEF 25% -75% (L/sec) were measured by spirometer for three times., and three indexes of FVC (L), FEV₁ (L) and FEF 25% -75% (L/sec) were recorded by spirometer for three times. Ask the patient if there are any adverse reactions, such as nausea, vomiting, itching, dizziness, headache, shoulder pain, respiratory depression, etc.

10) After returning to the ward, the patient can press the PCA for additional analgesia according to the needs. The patient was given rescue analgesia, a single use of diclofenac sodium suppository, if the pain was not relieved or the patient requested it. Investigators conducted postoperative visits at 2h, 4h, 8h and 24h postoperatively, the dosage of PCA, the times of rescue analgesia, VAS scores at rest and cough and adverse reactions were recorded. FVC (L), FEV1 (L) and FEF 25% -75% (L/sec) were recorded for three times by spirometer in the sitting position at 4h and 24h postoperatively. Patients were assessed postoperatively using the QoR-15 Patient Questionnaire at 24h postoperatively.

6. Outcome measurements

6.1 The primary outcome :

Cumulative morphine consumption at 24h postoperatively

6.2 The secondary outcomes:

- (1) The cumulative morphine consumption at 1h, 2h, 4h and 8h postoperatively.
- (2) The times of remedial analgesia at 1h, 2h, 4h, 8h and 24h postoperatively.
- (3) VAS score at rest and cough at 1h, 2h, 4h, 8h and 24h postoperatively.
- (4) The changes of FVC (L), FEV₁ (L) and FEF 25% - 75% (L / sec) were observed before operation, 1h, 4h and 24h after postoperatively.
- (5) Changes of QoR-15 questionnaire scores before and 24h postoperatively.
- (6) Postoperative complications and rehabilitation time nodes (including drainage tube removal time, discharge time, etc.).

7 Security

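### Prespecified covariate adjustment of 24h consumption is a cheap, optional gain in precision; the planned unadjusted comparison is valid without it

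*Combined protocol and SAP*

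**What the plan says.** All references are to the combined protocol and SAP.

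- **Allocation (section 3.3).** "Patients were allocated randomly to SAPB & ESPB group and PVB group according to computer-generated random number table". Block sizes, strata and minimisation are not mentioned.
- **Population (section 4.1).** The surgical criterion is "Selective thoracoscopic partial pneumonectomy under general anesthesia", with no limit on the extent of partial resection. Other criteria restrict ASA status to I-II, age to 18–75 years and BMI to 19–28 kg/m². Section 4.3 withdraws conversions to thoracotomy and operations longer than 4 hours.
- **Analysis (section 10).** "Measurement data were analyzed and compared by t-test or Mann-Whitney U test, depending on whether the data were distributed normally or not". The same section also gives morphine consumption as an example of data for one-way ANOVA. No covariate, ANCOVA or regression model appears anywhere.
- **Sample size (section 3.2).** "1:1 enrollment would require 41 patients in each group", at a "significance level of 0.05 for a one-sided test and performance test of 80" per cent. The effect is fixed as follows: "A difference of 2.5 mg in the 24h postoperative morphine consumption was chosen as the minimum expected difference between the two groups". The pilot values are "23.7 ± 4.8 mg in the SAPB & ESPB group" and "28.7 ± 4.2 mg in the PVB group".

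**The concern.** The target difference of 2.5 mg is small beside a pilot SD of about 4.5 mg, and the sample size leaves no spare power. Age, BMI and the extent of lung resection could plausibly affect opioid use. Age and BMI are already in hand when the patient is allocated, and planned extent could be noted at the visit the day before surgery (section 5). If none of them enters the allocation or the analysis, whatever variance they explain stays in the error term. A chance difference between the arms in these factors also goes uncorrected. What is at stake is the width of the confidence interval and a few points of power.

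**Working it through.** **Inputs.** From section 3.2: pilot SDs 4.8 and 4.2 mg, difference 2.5 mg, one-sided 0.05, 80% power, 41 per arm, 10% dropout. Assumed, because the documents give no figure: R² of 0 to 0.20, a 50% share of lobar resections, and 2–4 mg higher consumption after lobar resection.

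**1. The plan's own figure.** Pooled SD = √((4.8² + 4.2²)/2) = √20.34 = 4.51 mg. Then n = 2 × 20.34 × (1.645 + 0.842)² / 2.5² = 40.2, so 41 per arm. Total = 82/0.90 = 91.1, so 92. Both match the plan, with no allowance for covariates.

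**2. Which test is primary.** Section 10 can be read as a t-test, a Mann-Whitney test or one-way ANOVA. With two arms at one time point, one-way ANOVA is the equal-variance t-test. The primary comparison is unadjusted on every reading.

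**3. Chance imbalance.** For a factor present in half the patients, the SD of the between-arm difference is √(0.25 × 2/41) = 0.110. The chance of a gap above 10 percentage points is 0.37, and above 20 points 0.07. A 10-point gap with a 2–4 mg effect shifts the raw difference by 0.2–0.4 mg. The unadjusted standard error is 4.51 × √(2/41) = 0.996 mg, and that figure already contains this source of variation.

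**4. Power with adjustment.** SE = 4.51 × √(1 − R²) × √(2/41) × √(80/77). The last factor is the usual approximate charge for estimating three covariates under simple allocation. Power comes from the noncentral t with 77 df (80 df unadjusted) and noncentrality 2.5/SE.

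| Analysis | SE (mg) | Power, one-sided 0.05 | Power, two-sided 0.05 |
|---|---|---|---|
| Unadjusted | 0.996 | 80.1% | 69.8% |
| Adjusted, R² = 0 | 1.015 | 78.7% | 68.1% |
| Adjusted, R² = 0.05 | 0.990 | 80.5% | 70.4% |
| Adjusted, R² = 0.10 | 0.963 | 82.3% | 72.7% |
| Adjusted, R² = 0.20 | 0.908 | 86.1% | 77.6% |

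Break-even is where (1 − R²) × 80/77 = 1, an R² of about 0.04.

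**5. What those R² values require.** A 50% factor with effect d explains 0.25 × d²/20.34 of the variance: 5% for 2 mg, 11% for 3 mg, 20% for 4 mg. If resection worked alone, an R² of 0.10 would need an effect of √(0.10 × 20.34/0.25) = 2.85 mg, which is more than the treatment difference the trial is designed to detect. Age and BMI may add to this, but BMI is confined to 19–28.

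**The case against.** The strongest reply is that nothing here is broken. Under randomisation the unadjusted difference is unbiased and its test is valid. The sample size was calculated for that comparison and reproduces exactly. Adjustment was never needed to reach the stated power, and at an R² of 0.05 it gains less than one point. All of that stands.

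A reader might infer more than the documents support in three ways:

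- **That chance imbalance is a harm in addition to lost precision.** It is not. The 0.2–0.4 mg shift is ordinary sampling error, already counted in the standard error of about 1.0 mg.
- **That patients are an unrestricted mix, or that allocation is known to be unrestricted.** Eligibility is limited on ASA status, age, BMI and type of surgery, and only the extent of partial resection is open. A computer-generated table may or may not have been blocked; the protocol does not say.
- **That adjustment would remove the variance and imbalance.** It removes only the part the chosen covariates explain, and no figure in the documents links age, BMI or resection to consumption.

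What survives is a narrower argument. The possible loss is small and bounded, modest prognostic value repays it, and fixing the model in advance avoids a later argument about whether to adjust if an imbalance is seen.

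**Conclusion.** This is an optional improvement in precision and not a defect in the plan. Relative to the unadjusted test, the net effect on one-sided power runs from a loss of about 1.5 points (R² = 0) to a gain of about 6 points (R² = 0.20), with break-even near 0.04. Two-sided, the range is about −2 to +8 points. These figures assume 41 evaluable patients per arm, the pilot SD of 4.51 mg, a true difference of 2.5 mg and three covariates. The R² values have no source in the documents.

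Adjustment should not be read as a repair for the separate question of sidedness. Section 3.2 is one-sided, while section 10 gives a 0.05 threshold without saying which. If the test is two-sided, unadjusted power is about 70%, and adjustment at an R² of 0.20 still leaves it below 80%.

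**What to change.** Amend section 10, before those choosing the model see outcomes by arm:

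1. The primary analysis is a linear model of 24h cumulative consumption on arm, age and BMI, plus planned extent of resection (lobar versus smaller) if it is recorded before randomisation. Report the adjusted mean difference with its 95% CI.
2. If residuals are clearly non-normal, keep the model and use robust standard errors or a bootstrap CI, naming in advance which.
3. State that this model replaces both the t-test/Mann-Whitney wording and the one-way ANOVA wording for the primary outcome. Keep the unadjusted test as a sensitivity analysis.
4. Do not adjust for anything that arises after randomisation, such as actual operation duration.

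In section 3.3, state how the list was generated. If recruitment has not finished, the remaining list can use permuted blocks of varying size, stratified by planned resection, with that stratum in the model. Items 1–4 stand without this step.

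**Cost.** One model statement and, where feasible, a regenerated list. Planned extent of resection is not a recorded item at present, so it must be defined and captured before allocation. No extra patients are needed. The statistical cost is three degrees of freedom and about 1.5 power points if the covariates explain nothing.
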